8.0 Study Withdrawal/Discontinuation

Criteria for study withdrawal/discontinuation

- Drug-related toxicity
- Requirement for prohibited concomitant medications (see exclusion criteria)
- Pregnancy
- Request by subject to terminate treatment
- Clinical reasons believed to be life threatening by the physician, even if not addressed on the potential risk section

9.0 Statistical Considerations

Sample size justification: For aim 1, we will compare primary endpoint (OT) between each surgery group (RYGB and VSG) and the medical weight loss group. Based on the literature,²² we expect a 48.5% reduction in orthostatic tolerance (OT) after RYGB/VSG (normal baseline OT is 36.7 ± 7.3 (mean±SD) versus poor OT 18.9 ± 5.96 .²²) After weight loss, we estimated a $\approx 25\%$ reduction in OT (baseline 36.7 ± 7.3 to 27.5 ± 7). This is a 25% difference in OT between surgical versus medical weight loss. We need n=15 per group to have 90% power to detect the difference between 18.9 and 27.5 using SD of 7 with type I error rate of 0.05. We plan to enroll 15 subjects in each of the 3 groups. For aim 2, in visit 3 we will randomize these 30 RYGB/VSG subjects with 1:1 ratio to the Strattera and placebo groups. We will compare OT between the placebo and the Strattera groups. We expect that OT is 18.9 ± 5.96 (mean±SD) for the placebo group (similar to the surgery group in aim 1) and the Strattera group will improve by $\approx 50\%$ or 28.35 ± 7 (mean±SD). With 15 in each group in aim 2, we will have excellent (96%) power to detect the difference.

Data Analysis Plan: the primary analyses will focus on the comparison of the primary endpoint, OT. In aim 1 between RYGB vs. medical weight loss, and between VSG vs. medical weight loss; in aim 2: between Strattera versus placebo groups. Secondary endpoints include changes in hemodynamics (blood pressure, heart rate) during HUT and HUT+LBNP, orthostatic changes in plasma catecholamines, and MSNA. We will assess continuous outcomes for normality. If normality is violated, we will apply data transformation or non-parametric analysis methods. We will provide summary statistics for both numerical and categorical variables by study arms and assess comparability among randomization groups. In both aims, we will estimate the direct between-group difference by means with its 95% confidence interval (CI), which will be tested using either two-sample t-test or Wilcoxon Rank Sum test. A multivariate general linear model will be used to evaluate the group or treatment effects while adjusting the baseline measure of the endpoint. Model over fitting will be avoided using the rule of thumb of 10 observations per parameter in the model. Analyses of secondary endpoints and other exploratory analyses will be conducted similarly. We will test all hypothesis at the level of α =0.05. We will use SPSS for Windows (Version 22.0, SPSS, Chicago) and the open source statistical package R (version 3.4.3, R Core Team, 2017) for analyses (https://www.R-project.org.)

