4.0 Enrollment/Randomization

Recruitment and informed consent:

We will recruit obese patients that will undergo bariatric surgery and medical weight loss from the Vanderbilt Center for Weight Loss (VWL). The VWL clinic is the largest bariatric surgery facility in Tennessee and annually performs \approx 500 bariatric surgeries. We may also recruit persons willing to participate in the Jenny Craig weightloss program for 6 weeks. We will use research match and subject locator as well as an online pre-screening survey. We will use printed consent and e-consent to consent the subjects, for the two, parallel-arm, placebo-controlled portion of the study. We will randomize 1:1 to either placebo vs. the NE-transporter inhibitor, atomoxetine, at doses of 0.5 mg/kg/day.

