5.0 Study Procedures

Pre-screening survey: Potential participants may choose to complete a pre-screening survey that will better evaluate their eligibility. Subjects may complete the survey on their own or while in clinic.

Screening evaluation: Patient will be consented by phone. We will review the pre-surgical evaluation to assess for inclusion/exclusion criteria and we will invite to complete additional visits in the center for surgical weight loss or the autonomic cardiovascular suite.

Visit 1: Baseline (pre-surgery, RYGB/VSG) or pre-hypocaloric diet (medical weight loss).

Visit 2: After 10% weight loss. The time is variable (RYGB/VSG= 10-12 days; medical weight loss group= \sim 30-40 days).

Visit 3 (only for RYGB and VSG groups): 3-months after the bariatric procedure.

Visit 4 (only for RYGB and VSG groups): After 3-days on stable doses of Strattera (atomoxetine) vs. matching placebo. For the two, parallel-arm, placebo-controlled portion of the study. We will randomize 1:1 to either placebo vs. the NE-transporter inhibitor, Strattera (atomoxetine), at doses of 0.5 mg/kg/day.

Visits 1-4 specific procedures:

In supine position, we will measure: 1) plasma volume assessment; 2) continuous beat-to-beat blood pressure, and heart rate monitoring; 3) muscle sympathetic nerve activity (MSNA) with microneurography (at the physician's descretion), 4) blood volume assessment; and 5) supine plasma catecholamines and metabolites.^{2, 16} We will assess orthostatic tolerance using tilt table testing.^{17, 18} We will perform a 60° head-up tilt (HUT) for 30 min until pre-syncope (defined as systolic BP (SBP, mm Hg) <80 or SBP>90 and pre-syncopal symptoms (nausea, lightheadedness, dizziness).¹⁹ We will repeat plasma catecholamines at the end of the 30 min HUT and hemodynamic measurements throughout the HUT. The supine and 60° HUT plasma catecholamines will provide information on orthostatic-induced sympathetic neuro-hormonal activation. We will use the ratio dihydoxyphenylglycol (DHPG) to NE as the biomarker for NET inhibition as we previously reported.²⁰ We will repeat the serum pregnancy test (if applicable).

We will wait 24 hours to perform visits 1-4 if the patient has received IV fluids for clinical care.

Our primary endpoint (orthostatic tolerance, OT) is defined as the time between the start of the 30° HUT until pre-syncope

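### Aim 2 pools RYGB and VSG participants, but neither the specified randomisation nor the analysis model takes account of the procedure

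*Combined protocol and SAP*

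**What the plan says.** Section 9.0 (sample size) sets the size of the three groups: "We plan to enroll 15 subjects in each of the 3 groups". For Aim 2 it pools the two surgical groups: "in visit 3 we will randomize these 30 RYGB/VSG subjects with 1:1 ratio to the Strattera and placebo groups". The power statement follows: "With 15 in each group in aim 2, we will have excellent (96%) power to detect the difference". It uses one expected value for both operations: "We expect that OT is 18.9 ± 5.96 (mean±SD) for the placebo group".

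Section 4.0, which is headed for randomisation, gives only the ratio: "We will randomize 1:1 to either placebo vs. the NE-transporter inhibitor, atomoxetine". Section 5.0 (Visit 4) says the same: "We will randomize 1:1 to either placebo vs. the NE-transporter inhibitor, Strattera (atomoxetine". None of the three sections names a method of sequence generation, a block size, a stratification factor or minimisation.

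The data analysis plan in Section 9.0 keeps the operations apart in Aim 1: "In aim 1 between RYGB vs. medical weight loss, and between VSG vs. medical weight loss". In Aim 2 it compares drug with placebo by a two-sample t-test or Wilcoxon test, and adds a linear model that adjusts for the baseline value of the endpoint. Procedure is not listed as a covariate. The only other provision is a check, after the fact, of whether the randomised groups are comparable.

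**The concern.** RYGB and VSG are different operations, and the plan itself reports them separately on the same primary endpoint in Aim 1. In Aim 2 they are merged, and nothing stated keeps the mix of operations equal between atomoxetine and placebo. With only 30 participants, a noticeable chance imbalance is not rare.

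If OT at three months differs between the operations, an imbalance moves the unadjusted drug-placebo difference up or down. Even with perfect balance, a difference between operations that is left out of the model stays in the error term and costs precision. If procedure is added only after an imbalance has been seen, the adjustment becomes a data-driven choice. The operation is fixed months before allocation, so all of this can be avoided in advance, but the allocation itself cannot be repaired afterwards.

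**Working it through.** **Inputs from Section 9.0.** 15 RYGB and 15 VSG; planned arms of 15 and 15; placebo mean 18.9 (SD 5.96); atomoxetine mean 28.35 (SD 7); planned difference 28.35 − 18.9 = 9.45; alpha 0.05, taken as two-sided. The sample-size text gives no unit for OT; minutes are assumed, because the tilt is timed in minutes.

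**Step 1. Reproduce the stated power.** Use SD 7 in both arms.
- Standard error = 7 × √(2/15) = 2.56.
- 9.45 / 2.56 = 3.70, and Φ(3.70 − 1.96) = 0.959, which matches the stated 96%.
- The noncentral t gives 0.946 with SD 7 in both arms and 0.970 with SDs 5.96 and 7.

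**Step 2. Chance of imbalance in procedure, arms fixed at 15/15, no strata.** The number X of RYGB participants in one arm is hypergeometric (30 participants, 15 RYGB, 15 drawn), so P(X = k) = C(15,k)² / C(30,15), with C(30,15) = 155,117,520. Doubling the upper tail covers either arm.
- 9/6 or worse: 0.466
- 10/5 or worse: 0.143
- 11/4 or worse: 0.027

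**Step 3. Effect on the unadjusted difference.** Let d be the RYGB-VSG difference in mean OT. With a 10/5 split the share of RYGB is 10/15 in one arm and 5/15 in the other, so the shift is d × (10 − 5)/15 = d/3. The documents give no value for d; 3 to 6 min is an assumption.

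| Assumed d | Shift at 10/5 | Shift / SE of 2.56 | Power if the shift opposes the drug (t, SD 7) |
|---|---|---|---|
| 3 min | 1 min | 0.39 | 0.89 |
| 6 min | 2 min | 0.78 | 0.80 |

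The last column compares with 0.946 for a balanced split. If the shift favours the drug, the estimate is too high by the same amount.

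**Step 4. Typical rather than tail size.** The SD of X is √(15 × 0.5 × 0.5 × 15/29) = 1.39, so the SD of the shift is d × 2 × 1.39/15 = 0.186d. That is 0.56 min for d = 3 and 1.1 min for d = 6.

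**Step 5. Precision with perfect balance but procedure left out.** Taking SD 7 within each procedure, the SD in the pooled arm is √(7² + d²/4). For d = 6 this is √58 = 7.6, and t power falls from 0.946 to 0.91. For d = 3 it is 7.16, with power 0.94.

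**Step 6. Unequal arm sizes alone.** With t and SD 7, power is 0.946 at 15/15, 0.945 at 16/14, 0.938 at 18/12 and 0.920 at 20/10. Under simple 1:1 allocation, exactly 15/15 has probability C(30,15)/2³⁰ = 0.144, and 18/12 or worse has probability 0.36, but power averaged over all splits is still 0.938.

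**The case against.** The strongest reply has four parts.

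- **Silence is not exclusion.** A reader might infer that the plan has decided against stratification or blocking. It has not: it says only 1:1, and its reference to 15 in each group is compatible with blocked allocation. This stands, and the point is therefore that stratification is not specified.
- **Aim 1 does not test RYGB against VSG.** A reader might infer that Aim 1 is built to detect a difference between the operations at three months. It compares each operation with medical weight loss, and the medical group has no three-month visit (Section 5.0). Section 2.0 states one joint hypothesis for both operations, and Section 9.0 assumes one OT value for both. This also stands. The documents do not show that the operations differ in OT; they show only that the plan keeps them apart in one aim and merges them in the other.
- **The shift is modest and random.** Even the 10/5 case moves the estimate by less than 0.8 of a standard error under the assumed 3 to 6 min. This stands, and it limits the weight of the point.
- **Baseline adjustment may already help.** OT is measured at Visit 3. If that value is the Aim 2 baseline, the model would absorb part of any difference between operations, and d/3 would overstate the shift in the adjusted estimate. This is possible but not certain: baseline is not defined for Aim 2, Section 5.0 gives that label to Visit 1, and the t-test or Wilcoxon comparison is unadjusted in any case.

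None of this is a reason to leave out a balancing step that needs no extra patients.

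**Conclusion.** The point holds as an inexpensive improvement, not as an error that undermines Aim 2. Nothing in the plan commits anyone to balancing procedure at randomisation or to adjusting for it in the analysis. If the arms are 15/15 and unstratified, a 10/5 or worse split occurs 14% of the time, and a 10/5 split moves the unadjusted difference by d/3. That is 1 to 2 min if d is 3 to 6 min, against a planned 9.45. The probability rests on the planned numbers; the minutes rest on an assumed d.

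Two stronger conclusions are not supported. One is that the Aim 2 result would be biased: the imbalance is random, so it is not systematic bias, and the type I error of the randomised comparison is preserved. The other is that the trial would be underpowered because 15 per arm is not guaranteed: the stated 96% reproduces, and unequal arms alone cost very little (0.938 at 18/12).

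**What to change.** In Sections 4.0 and 9.0, state how the sequence is generated and stratify the Aim 2 randomisation by procedure, using small permuted blocks. With block sizes of 2 and 4, for example, 15 participants within a procedure always split 8/7. The arms then total 15/15 or at worst 16/14, and the share of RYGB differs between arms by at most 1/15.

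In the data analysis plan, pre-specify the Aim 2 model with treatment, baseline OT and procedure, and say which visit supplies the baseline. Treatment, baseline OT and procedure are three parameters for 30 participants. This meets the plan's own rule of ten observations per parameter if the intercept is not counted and all 30 provide data; with any loss the rule is narrowly missed, so the plan should say that the three terms are kept regardless.

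The cost is two allocation lists instead of one, a sentence in each of the two sections and one model term. No participants or visits are added, and the power is essentially unchanged (0.946 at 15/15, 0.945 at 16/14). The change in allocation has to be made before Aim 2 randomisation; the model term should be fixed before unblinding.

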2.0 Specific Aims

Specific Aim 1: To test the hypothesis that bariatric surgery (RYGB and VSG) impairs sympathetic vasoconstrictor activity and lead to the development of orthostatic intolerance independent of weight changes.

Specific Aim 2: To test the hypothesis that potentiating sympathetic vasoconstrictor activity will reverse the impaired orthostatic tolerance post-bariatric surgery.

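### Do the two primary comparisons in Aim 1, each at 0.05, need a multiplicity adjustment or a combination rule?

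*Combined protocol and SAP*

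**What the plan says.** Section 2.0 states Aim 1 as one directional hypothesis: "bariatric surgery (RYGB and VSG) impairs sympathetic vasoconstrictor activity and lead to the development of orthostatic intolerance".

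The sample size paragraph of Section 9.0 turns this into two contrasts: "we will compare primary endpoint (OT) between each surgery group (RYGB and VSG) and the medical weight loss group". It sizes one of them: "We need n=15 per group to have 90% power to detect the difference between 18.9 and 27.5", with SD 7 and type I error 0.05. The Data Analysis Plan names the same two contrasts as primary, "In aim 1 between RYGB vs. medical weight loss, and between VSG vs. medical weight loss", and sets one level throughout: "We will test all hypothesis at the level of" 0.05. Each between-group difference is to be given with a 95% confidence interval and tested by a two-sample t-test or a Wilcoxon rank sum test.

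The document gives no multiplicity adjustment, testing order, pooled surgery comparison or joint power. It also does not say whether one or both contrasts must be significant for Aim 1 to be supported.

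**The concern.** One hypothesis is tested by two primary comparisons that share a control group, each at the full 0.05. If either significant result were taken to establish the statement about bariatric surgery, the error rate for that statement would be almost twice that of a single test.

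A split result is also not rare. Even if the planning assumptions are exactly right, about one trial in eight would find one operation significantly different from medical weight loss and the other not. Without a rule, the investigators could decide after seeing the data whether such a result supports the general claim. And if both comparisons were required, the chance of success would be below the 90% quoted for each.

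**Working it through.** **Inputs, all from Section 9.0.** Difference 27.5 − 18.9 = 8.6; SD 7; 15 per group; two contrasts with a shared control; level 0.05. Sidedness is not stated.

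**1. The plan's own figure.** Standardised difference 8.6/7 = 1.229. The two-sided t-test at 0.05 (noncentral t, 28 degrees of freedom) needs n = 14.95 per group, so 15, and power at 15 is 90.1%. A one-sided 0.05 test would need only about 12 to 13. The plan's figure therefore reproduces as a two-sided test of one contrast, which puts 2.5% in the direction of lower OT.

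**2. Error if neither operation differs from medical weight loss.** With equal groups and a common control, each mean difference has variance 2σ²/15 and their covariance is σ²/15, so the correlation is 0.5. From the bivariate normal, P(both falsely lower) = 0.0046. Then:

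- Either falsely lower: 0.025 + 0.025 − 0.0046 = 0.0454.
- Either significant in any direction: 0.0907.
- Both falsely lower: 0.0046.

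Simulating 2,000,000 trials with t-tests gave 0.0454, 0.0906 and 0.0046.

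**3. What each reading of Aim 1 implies.**

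| Reading | False lower-OT finding | Adjustment needed? |
|---|---|---|
| Two procedure-specific conclusions | 2.5% for each | No |
| Both must be significant | 0.46% if neither operation has an effect; at most 2.5% if one has | No |
| One significant test is enough | 4.5% | Yes |

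Only the third row is inflated, and no sentence in the document adopts it.

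**4. Under the planned effects (18.9 in both surgical groups, 27.5 in the medical group, SD 7).** In simulation each contrast is significant in 90.1% of trials, at least one in 96.8% and both in 83.5%. Split results: 96.8% − 83.5% = 13.3%. The plan gives the surgical groups a smaller SD ("versus poor OT 18.9 ± 5.96"). With 5.96 there, power is 93.8% for each and 89.6% for both, and split results fall to 2 × (93.8% − 89.6%) = 8.4%.

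**5. What an adjustment would bring.** Under Hochberg's procedure both contrasts are significant if both p-values are below 0.05; otherwise the smaller must be below 0.025. At SD 7:

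- Any false lower-OT finding falls from 4.5% to 2.4%.
- Power for each contrast falls from 90.1% to 88.8% under the planned effects.
- If only one operation has an effect, power for it falls from 90.1% to 83.8%, a loss of 6.3 points. In that case exactly one contrast shows significantly lower OT in about 81% of trials with Hochberg and about 88% without.
- Unadjusted 95% intervals would sometimes exclude zero where Hochberg does not reject: 2.7% of trials under the planned effects and 6.8% if only one operation has an effect.

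**6. Sensitivity.** These figures assume normally distributed OT without a ceiling. Section 5.0 describes a "head-up tilt (HUT) for 30 min until pre-syncope". If OT were capped at 30 minutes, power for each contrast at SD 7 would be 88.3% unadjusted and 86.7% with Hochberg. With 13 completers per group (an assumption) and no cap, the figures are 85.2% and 83.1%. These cases change the power of each contrast but not how the two contrasts relate to Aim 1.

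**The case for a change.** The strongest case for a change is that Section 2.0 states a single hypothesis, that Section 9.0 does not say how two results bear on it, and that a split result is an ordinary outcome. One sentence would remove any room for choosing the interpretation after the data are in, at no cost in patients or visits. Each reading that yields a single conclusion also has a consequence: a raised error rate if one test is enough, or a chance of success near 83% if both are required.

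The arithmetic behind this stands, and so does the observation that the rule is unwritten. The inference that the plan is therefore in error does not. Section 9.0 says each surgery group is compared with medical weight loss, lists the two contrasts by name, sizes each, and defines no combined surgery result. That is most naturally read as two answers, one per operation. If Section 2.0 is instead taken literally, its wording joins the two operations with *and*, which points to requiring both. Neither reading inflates the error, and the plan claims no joint power that a requirement for both would contradict.

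Nor does an adjustment meet the worry behind the concern. If one significant test were allowed to support the claim about bariatric surgery, Hochberg's procedure would still allow it. With an effect of only one operation, that would happen in about 81% of trials, each counted in favour of a hypothesis that names both operations. What limits overstatement is reporting the two contrasts separately, which the plan already provides for. Statisticians differ on whether to adjust for two distinct procedures compared with a common control. Here Aim 1 is also a comparison of non-randomised groups, since randomisation applies only to atomoxetine versus placebo, so strict familywise control adds little to the strength of the inference.

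**Conclusion.** The concern does not call for a change. Followed as written, the plan gives two pre-declared, procedure-specific comparisons, each with 5% two-sided error and about 90% power at SD 7, and each with its own estimate and interval. The figure of 9.1% against 5% (4.5% against 2.5% for falsely lower OT) applies only if one significant test is taken to prove the general statement, which the document does not say. What is missing is an interpretive detail that analysts can fill sensibly: report RYGB and VSG separately, and do not extend one significant result to bariatric surgery as a whole. An adjustment would be a trade-off, costing 1.3 points of power under the planned effects and 6.3 points if only one operation has an effect, without settling how a split result is read.

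The conclusion rests on two-sided testing, which is inferred from the sample size. The figures further assume normal OT, pooled t-tests, 15 analysed per group and SD 7. Aim 2 is a separate hypothesis and is not affected.

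### The primary test of orthostatic tolerance is left to a normality check while the interval is always for a difference in means, so p-value and CI can address different quantities and disagree

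*Combined protocol and SAP*

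**What the plan says.** The Data Analysis Plan in section 9.0 of the combined protocol and SAP makes OT the primary endpoint for both aims. It then states "We will assess continuous outcomes for normality" and "If normality is violated, we will apply data transformation or non-parametric analysis methods". It does not say which normality test or threshold applies, whether the check is made per arm, on pooled data or on residuals, which transformation would be used, or whether transformation or a rank method comes first.

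For the effect size, the plan says "we will estimate the direct between-group difference by means with its 95% confidence interval (CI" and, of that same difference, "which will be tested using either two-sample t-test or Wilcoxon Rank Sum test". A further analysis follows: "A multivariate general linear model will be used to evaluate the group or treatment effects while adjusting the baseline measure of the endpoint". Its rank against the unadjusted test is not stated. The level is 0.05 for every hypothesis; sidedness is not given.

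Two other statements bear on how OT will be distributed. Section 5.0 says "We will perform a 60° head-up tilt (HUT) for 30 min until pre-syncope", but gives no OT value for a subject who completes the tilt without pre-syncope. Section 9.0 refers to hemodynamics during HUT+LBNP, a procedure that section 5.0 does not describe.

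**The concern.** A confirmatory analysis should be one test with the estimate and interval that belong to it. Here the test is settled only after the outcome has been examined, but the interval is fixed in advance as one for a difference in means. Wilcoxon does not test a difference in means, and a t-test on a transformed scale does not match a raw-scale interval either. No Hodges-Lehmann estimate or back-transformation is provided for. A report could therefore show a significant p-value beside a CI that includes zero, or the reverse, with nothing in the plan to say which one decides.

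The fallback may also be the usual route. If tilt completers were scored at 30 minutes, a large share of some arms would sit at a single value. A normality test would then nearly always reject, and no monotone transformation removes such a pile-up.

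**Working it through.** **Inputs (section 9.0).** Aim 1: 18.9 versus 27.5, SD 7, n=15 per group, 90% power. Aim 2: 18.9 ± 5.96 versus 28.35 ± 7, n=15 per group, 96% power. Baseline OT is 36.7 ± 7.3. I take alpha as two-sided 0.05 and OT as minutes.

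**Reproducing the plan's power.** Two-sample t-test, noncentrality = (difference/SD) × √(n/2).
- Aim 1: (8.6/7) × √7.5 = 3.36, giving power 90.1%; the required n is 14.95, so 15. This agrees with the plan.
- Aim 2: root-mean-square SD = √[(5.96² + 7²)/2] = 6.50; (9.45/6.50) × √7.5 = 3.98, giving 97.0%. With SD 7 it is 94.6%. The stated 96% lies between.

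**Share of subjects at an assumed 30-minute ceiling**, P(OT > 30) under normality:
- medical weight loss: z = (30 − 27.5)/7 = 0.36, so 36%
- Strattera: z = (30 − 28.35)/7 = 0.24, so 41%
- surgery or placebo: z = (30 − 18.9)/5.96 = 1.86, so 3%
- baseline: z = (30 − 36.7)/7.3 = −0.92, so 82%

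**How often the check would fire.** Assume Shapiro-Wilk at 0.05 in each arm. Without a ceiling it rejects in at least one arm in about 9% of trials (two independent tests: 1 − 0.95² = 9.75%). With the ceiling it rejects in about 83% (aim 1) and 91% (aim 2) of trials at the planned effects.

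**Type I error.** Simulation, 15 per group, both groups from the same distribution, capped at 30, Monte Carlo standard error 0.18 points. The last two columns keep the smallest p-value. The four methods are t on raw OT, log and a second transformation (square) as examples, and Wilcoxon.

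| Null distribution | t only | Wilcoxon only | Check, then t or Wilcoxon | Smallest p of t, Wilcoxon | Smallest p of four |
|---|---|---|---|---|---|
| Normal 18.9, 5.96 | 5.1% | 4.5% | 5.2% | 5.7% | 6.7% |
| Normal 27.5, 7 | 4.8% | 4.6% | 5.0% | 6.1% | 6.4% |
| Normal 36.7, 7.3 | 2.5% | 4.3% | 4.3% | 5.3% | 5.4% |
| Exponential (assumed) | 5.1% | 4.5% | 5.3% | 5.6% | 7.9% |
| Lognormal (assumed) | 5.1% | 4.5% | 5.2% | 5.7% | 7.2% |

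Moving the check between residuals, pooled data and each arm gave 4.1–5.1% under the three capped normal nulls, and 4.8–5.0% for normal 18.9, 5.96 without a cap. Repeat runs of the two-step rule lay between 4.2% and 5.5%. Inserting a log step before Wilcoxon, still applied mechanically, gave 4.3–5.2% under the tabulated normal nulls and 5.5–6.1% under the two skewed ones.

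**Disagreement between test and interval.** The t-based 95% CI for the mean difference excludes zero exactly when the t-test is significant. The rate at which t and Wilcoxon disagree is therefore the rate at which that CI and a Wilcoxon p-value conflict.

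| Scenario | All trials | Trials where the check fires and they disagree |
|---|---|---|
| Aim 1 effect, cap 30 | 4.2% | 3.0% |
| Aim 2 effect, cap 30 | 2.0% | 1.6% |
| Difference of 5 (22.5 vs 27.5), cap 30 | 7.8–8.5% | 6.9% |
| Aim 1 effect, no cap | 4.1% | 0.5% |

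**Power.** Aim 1 with the cap: t 88.0%, Wilcoxon 86.9%. Aim 1 without it: t 90.4%, Wilcoxon 87.7%. Aim 2 with the cap: about 95% for either.

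**The case against.** The strongest objection is that the plan's operating characteristics are sound if it is followed straightforwardly: t-test if the check passes, Wilcoxon if not. That stands. A reader might infer that a tilt ceiling drives the error rate above 0.05. It does not: under the ceiling the two-step rule stays at about 4% to 5.5%, and a heavy ceiling makes the t-test conservative. A reader might also infer that the plan permits choosing by p-value, or that it inspects the data by group. The text says neither. It is silent on the options, and the inflated figures describe deliberate selection among transformations that I supplied.

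The ceiling is also an inference. Section 5.0 gives the tilt duration but no score for completers, the planning baseline of 36.7 exceeds 30, and section 9.0 mentions HUT+LBNP. Without a cap the check would seldom fire, and conflicts in trials where Wilcoxon is actually used fall to about 0.5% at the aim 1 effect. Finally, the difference of 5 is not a planning value; it illustrates a borderline result.

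The objection does not remove the textual defect. The plan names no single primary analysis, and it attaches a mean-difference interval to a test that may not concern means. The simulations also show that the check buys little: the fixed t-test does not exceed about 5% under any null tried, capped or skewed.

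**Conclusion.** The point holds as a defect of pre-specification and of matching test to interval. It is modest in size and cheap to repair. Under an assumed 30-minute cap, the CI and a Wilcoxon p-value disagree on significance in about 4% of aim 1 trials and 2% of aim 2 trials at the planned effects, and in about 8% at a difference of 5. Such conflicts matter most when the result is close.

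The documents do not support the stronger statement that alpha is exceeded. The defensible statement is that the wording does not by itself fix alpha, because the rule is not fully specified. Selective use of the open options could take it to about 6–7% with capped normal data and up to about 8% in assumed skewed scenarios, as a worst case. These figures rest on Shapiro-Wilk at 0.05, normal OT truncated at 30, log and square as example transformations, and the tie-corrected asymptotic Wilcoxon.

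**What to change.** Drop the normality check for OT, and name one primary analysis per aim before any outcome is seen, with the CI taken from that same analysis. A natural choice is already in section 9.0: the baseline-adjusted difference in means, with its own p-value and CI, or with a permutation p-value. For example:

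*For each aim 1 contrast and for aim 2, the primary analysis of OT is the group difference from a linear model adjusting for baseline OT, with its two-sided p-value and 95% CI. The Wilcoxon rank sum test with the Hodges-Lehmann estimate and CI is a sensitivity analysis, and no normality test will alter this choice.*

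The model has three parameters (intercept, group, baseline) for 30 subjects per comparison, which meets the plan's own rule of 10 observations per parameter. The text should name the visit that supplies the baseline for each aim and state how tilt completers are scored. If OT is capped at 30, about 82% of baseline values would be at the cap, and the adjustment would then add little.

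The cost is two sentences. Power is little affected if the mean-based analysis is primary. Choosing Wilcoxon instead would cost about 1 point at the aim 1 effect with the cap (88.0% to 86.9%) and somewhat over 2 without it (90.4% to 87.7%). If many subjects complete the tilt, a pure location shift no longer describes the data. Hodges-Lehmann intervals and intervals from inverting a permutation test are then only approximate, and the report should say so.
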